9.5.3. Ramucirumab

Doses will be delayed or reduced for clinically significant toxicities that are related to ramucirumab. In case of a dose delay of ramucirumab, patients can continue LY2157299 treatment (at the investigator's discretion).

9.5.3.1. Infusion-Related Reactions

Reduce the ramucirumab infusion rate by 50% for the duration of the infusion and all subsequent infusions if the patient experiences a Grade 1 or 2 infusion-related reaction (IRR) (per the NCI CTCAE). Premedication is recommended with an IV histamine H1 antagonist (eg, diphenhydramine) prior to administration of ramucirumab.

If a patient experiences a Grade 1 or 2 IRR, premedication **must** be given for all subsequent infusions. If a patient has a second Grade 1 or 2 IRR, administer dexamethasone (or equivalent); then, for subsequent infusions, premedicate with the following or equivalent medications: diphenhydramine hydrochloride (intravenously), acetaminophen, and dexamethasone.

Immediately and permanently discontinue ramucirumab for Grade 3 or 4 IRRs.

9.5.3.2. Hypertension

Monitor blood pressure during treatment with ramucirumab and treat as clinically indicated. Temporarily suspend ramucirumab for severe hypertension until controlled with medical management.

9.5.3.3. Proteinuria

Monitor for the development or worsening of proteinuria during ramucirumab therapy. If the urine protein level is $\geq 2+$, perform a 24-hour urine collection. Temporarily discontinue ramucirumab administration if the urine protein level is ≥ 2 g/24 hours. Resume treatment at a reduced dose level (see [Table JBAK.9](#)) once the urine protein level returns to < 2 g/24 hours. A second dose reduction (see [Table JBAK.9](#)) is recommended if a urine protein level ≥ 2 g/24 hours reoccurs.

Permanently discontinue ramucirumab therapy if the urine protein level is > 3 g/24 hours or in the setting of nephrotic syndrome.

Table JBAK.9. Ramucirumab Dose Reductions for Proteinuria

Initial Ramucirumab Dose	First Dose Reduction to:	Second Dose Reduction to:
8 mg/kg	6 mg/kg	5 mg/kg

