9.1.3. Part D

Part D comprises 2 dose-escalation cohorts and involves characterization of LY2157299 administered at either 80 mg BID or 150 mg BID for 14 days followed by 14 days off and ramucirumab 8 mg/kg on Days 1 and 15 of each cycle administered as an IV infusion over approximately 60 minutes (maximum infusion rate: 25 mg/min). On Day 1 of each cycle, LY2157299 should be taken within 30 minutes before the start of ramucirumab treatment.

LY2157299 should be taken mornings and evening approximately 12 hours apart; ramucirumab should be given in the mornings.

A cycle is defined as 28 days. [Table JBAK.5](#) shows the proposed dose levels and schedule for Part D.

Table JBAK.5. Treatment Regimens for Part D

	Dose	Schedule	Time of Day
Cohort 1	80 mg BID LY plus	Daily by oral administration 14 days on/14 days off	Morning and evening for 14 days and then paused for 14 days.
	8 mg/kg ramucirumab	Days 1 and 15 each cycle by IV administration (given over 60 min)	On Day 1 of each cycle, morning within 30 min of LY2157299 administration; on Day 15 of each cycle, morning
Cohort 2	150 mg BID LY plus	Daily by oral administration 14 days on/14 days off	Morning and evening for 14 days and then paused for 14 days.
	8 mg/kg ramucirumab	Days 1 and 15 each cycle by IV administration (given over 60 min)	On Day 1 of each cycle, morning within 30 min of LY2157299 administration; on Day 15 of each cycle, morning

Note: For patients who will have a Day 15 PK sample taken, the evening dose on Day 14 will be omitted to allow for a 24-hour time period between the Day 14 morning dose and the Day 15 PK sample.

In extenuating circumstances, the on-study-drug window for LY2157299 is allowable from Day 10 to Day 14. Abbreviations: BID = twice daily; IV = intravenous; LY = LY2157299; min = minutes; PK = pharmacokinetic.

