9.9. Treatment Compliance

Patient compliance with study medication will be assessed at each visit. Compliance will be assessed by direct questioning, review of diary, and counting returned tablets. Deviations from the prescribed dosage regimen should be recorded in the "Study treatment: modifications" form.

For patients who are significantly noncompliant (<80% or >120% of expected study drug taken in a visit interval), investigative sites must counsel patients on the importance of study drug compliance and drug accountability. Patients who are consistently out of the compliance range may be discontinued. A Lilly representative should be contacted upon the second instance of treatment noncompliance.

The following procedures will be employed to assure appropriate drug accountability:

- Drug accountability will be emphasized at the start-up meeting.
- Drug accountability will be monitored throughout the study.
- Each patient should be instructed to return all study-drug packaging and unused material to the study site at each visit. The study site will keep a record of all drug dispensed to and returned by the patients throughout the study. Study site personnel will return or destroy (as requested) all unused study drug for all patients.
- Patients will keep a study diary to document that they are taking LY2157299 and sorafenib (if applicable) correctly.

Ramucirumab in Part D will be administered intravenously at the investigational site, under the direction of the investigator. As a result, a patient's compliance with study drug administration is ensured.

10. Efficacy, Health Outcome/Quality of Life Measures, Safety Evaluations, Sample Collection and Testing (Standard Laboratory Testing, Pharmacokinetics, Biomarker Analysis), and Appropriateness of Measurements

Refer to the Study Schedule in [Attachment 1](#) for study procedures and their timing.

Terms used to describe the study periods are defined below:

- **Baseline/Visit 0:** From the time of screening to first study treatment (or discontinuation, if no treatment is given)
- **Treatment Start:** First day of study treatment
- **Study Treatment Period:** Time from treatment start to discontinuation from study treatment
- **Discontinuation from Study Treatment:** The day the patient discontinues study treatment (summary visit)
 - **Applies to patients in extension period, too**

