Attachment 1. Protocol JBAK Study Schedule

Parts A and B

Cycle/Visit ^j	Prestudy			Cycle 1					Cycle 2		Cycle 3, n ^l		Extension Period	Visit 801	Follow-up ^f	Comments
	≤28	≤14	≤7	1 ⁱ	8 ⁱ	14 ⁱ	15	22	1 ⁱ	14 ^{i,k}	1 ⁱ	14 ^{i,k}				
Procedures																
Informed Consent	X															Informed consent must be signed prior to performing any study procedures.
Medical History		X														
Child-Pugh, Barcelona Clinic Liver Cancer (BCLC), and CLIP staging			X ^h													
Pregnancy Test			X													
Physical Exam		X		X		X			X	X	X		X	X		Starting in Cycle 3, to be performed once per cycle. Perform predose on Day 1 of each cycle in extension period.
Vital Signs (heart rate, blood pressure)		X		X		X			X	X	X		X	X		Starting in Cycle 3, to be performed once per cycle. Perform predose on Day 1 of each cycle in extension period.
CTCAE Grading		X		X		X			X	X	X		X	X	X ^a	Starting in Cycle 3, to be performed once per cycle. Perform predose on Day 1 of each cycle in extension period.
Concomitant Medications		X		X					X		X		X	X	X	Perform predose on Day 1 of each cycle in extension period.
Performance Status		X		X		X			X	X	X		X	X		Starting in Cycle 3, to be performed once per cycle. Perform predose on Day 1 of each cycle in extension period.

Cycle/Visitj	Prestudy			Cycle 1					Cycle 2		Cycle 3, n ^l		Extension Period	Visit 801	Follow-up ^f	Comments
	≤28	≤14	≤7	1 ⁱ	8 ⁱ	14 ⁱ	15	22	1 ⁱ	14 ^{i,k}	1 ⁱ	14 ^{i,k}				
Tumor Assessment, Physical (Palpable or Visible)		X		X					X		X			X		Optional during the extension period (including extension period V801)
Imaging Procedures																
Echocardiography with Doppler ^g	X								X		X		X	X ^b	X ^b	Cycle 2, 3, 4, and every other cycle (C6, C8,...etc). Perform predose on Day 1 of each cycle in extension period
Chest CT Scan or Chest MRI		X											X	X ^c		CT scan or MRI every 6 months
Tumor Assessment, Radiological		X								X	X			X ^d	X ^d	Tumor assessment every 6 weeks starting Cycle 2, Day 14. May be performed 3 days around the scheduled date. Optional during the extension period (including extension period V801)
ECG		X							X		X		X	X ^b	X ^b	Cycle 2, 3, 4, and every other cycle (C6, C8,...etc). Perform predose on Day 1 of each cycle in extension period

Cycle/Visit ^j	Prestudy			Cycle 1					Cycle 2		Cycle 3, n ^l		Extension Period	Visit 801	Follow-up ^f	Comments
	≤28	≤14	≤7	1 ⁱ	8 ⁱ	14 ⁱ	15	22	1 ⁱ	14 ⁱ , k	1 ⁱ	14 ⁱ , k				
Laboratory /Diagnostic Tests																

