- f Follow-up consists of Visit 802 and all subsequent visits (60 days ±7 days). For the patients in the extension phase, long-term follow up will not be conducted unless there are cardiac toxicities (Section 10.2.4).

- g Echocardiography with Doppler can be performed up to 3 days prior to Day 1.
- h Child-Pugh, BCLC, and CLIP assessment procedures can be found in [Attachment 5](#), [Attachment 6](#), and [Attachment 7](#), respectively.
- i To be performed predose LY2157299 or sorafenib.
- j A delay at the start of a cycle (Day 1) of no more than 3 days, because of holidays, weekends, inclement weather, or other justifiable events, will be permitted and not counted as a protocol violation.
- k In extenuating circumstances, the “on study drug” window for LY2157299 is allowable from Day 10 to Day 14.
- l Patients on study for more than 1 year (before entering extension phase) only need tests to be performed on Day 1 of each cycle.

Part D

Cycle/Visit ⁱ	Prestudy			Cycle 1							Cycle 2				Cycle 3, n ^l		Extension Period	Visit 801	Follow -Up ^f	Comments
	≤28	≤14	≤7	1 ⁱ	8 ⁱ	14 ⁱ	15	22	23	27	1 ⁱ	14 ^{i,k}	15	22	1 ⁱ	14 ^{i,k}				
Procedures																				
Informed consent	X																		Informed consent must be signed prior to performing any study procedures	
Medical history		X																		
Child-Pugh, Barcelona Clinic Liver Cancer (BCLC), and CLIP staging			X ^h																	
Pregnancy test			X																	
Physical exam		X		X		X					X	X			X		X	X	Starting in Cycle 3, to be performed once per cycle. Perform predose on Day 1 of each cycle in extension period	
Vital signs (heart rate, blood pressure)		X		X		X					X	X			X		X	X	Starting in Cycle 3, to be performed once per cycle. Perform predose on Day 1 of each cycle in extension period	
CTCAE grading		X		X		X					X	X			X		X	X ^a	Starting in Cycle 3, to be performed once per cycle. Perform predose on Day 1 of each cycle in extension period	
DLT assessment									X											
Concomitant medications		X		X							X				X		X	X	Perform predose on Day 1 of each cycle in extension period	

Cycle/Visit ^j	Prestudy			Cycle 1							Cycle 2				Cycle 3, n ^l		Extension Period	Visit 801	Follow -Up ^f	Comments
	≤28	≤14	≤7	1 ⁱ	8 ⁱ	14 ⁱ	15	22	23	27	1 ⁱ	14 ^{i,k}	15	22	1 ⁱ	14 ^{i,k}				
Performance status		X		X		X					X	X			X		X		Starting in Cycle 3, to be performed once per cycle. Perform predose on Day 1 of each cycle in extension period	

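### Part D bases ramucirumab dose rules mainly on urine protein, yet every Day 15 infusion rests on a scheduled urine result about 14 days old or older

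*Protocol*

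**What the plan says.** Protocol Section 9.1.3 gives "ramucirumab 8 mg/kg on Days 1 and 15 of each cycle administered as an IV infusion", so each 28-day cycle has two infusions.

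Section 9.5.3.3 opens with "Monitor for the development or worsening of proteinuria during ramucirumab therapy". A urine protein of 2+ or more leads to a 24-hour collection. Two rules then act on the 24-hour value. "Temporarily discontinue ramucirumab administration if the urine protein level is" 2 g/24 hours or more, with resumption at a reduced dose (8 to 6 to 5 mg/kg). "Permanently discontinue ramucirumab therapy if the urine protein level is" above 3 g/24 hours; nephrotic syndrome is the one other ground for stopping. The section gives no testing frequency and does not ask for a value before each infusion.

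The opening of Section 10 sends sites to Attachment 1 "for study procedures and their timing". In the Part D table the urinalysis row is marked in four places: the screening column for the 14 days before dosing, Cycle 2 Day 1, Day 1 of Cycle 3 and later cycles, and Visit 801. Nothing is marked during Cycle 1 or on any Day 14, 15 or 22. Urinalysis is optional in the extension period. Footnote m concerns eligibility only. Footnote l limits tests to Day 1 of each cycle after one year on study.

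**The concern.** The dosing rules need a urine protein value, and the timing table supplies one every 28 days against a 14-day infusion interval. A site that follows Attachment 1 exactly can give a Day 15 infusion that Section 9.5.3.3 would have held, because no scheduled test would have revealed the proteinuria.

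The second consequence concerns dose escalation. Under Section 9.1.5.1 a related nonhematological toxicity of Grade 3 or worse in Cycle 1 is a DLT, and proteinuria is not among the exceptions. Under Section 7.1 the difference between no DLT and one DLT in the first three patients decides whether a cohort needs three more. An event that no scheduled test looks for is easily left out of that count.

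The urinalysis marks for Part D are the same as those for Parts A and B and for Part C. This suggests that the row was carried over without being adapted to a drug given every 14 days with urine-based dose rules.

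**Working it through.** The plan states no figure to reproduce here, so the check is a count from the schedule.

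**Inputs**
- Infusions on Days 1 and 15 (Section 9.1.3).
- Nominal cycle of 28 days, allowed range 26 to 31, and a planned duration of 6 cycles (Section 7.1).
- Part D urinalysis marks: screening (14 days or less before dosing), Day 1 of Cycles 2 onward, Visit 801 (Attachment 1).
- Alignment check: read by the same columns, the Part D PK row falls on Days 1, 14 and 15 of Cycles 1 and 2, as Section 10.3.2 says it should.

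**Age of the last scheduled urine result at the Day 15 infusion**

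Count days from Cycle 1 Day 1 = 0. The Day 15 infusion of cycle c falls on day 28(c − 1) + 14.
- Cycles 2 and later: the last scheduled urinalysis is on day 28(c − 1). Age = 14 days.
- Cycle 1: the last scheduled urinalysis is at screening, between day −14 and day 0. Age = 14 − (−14) = 28 days at most and 14 − 0 = 14 days at least.

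Because cycle lengths and visit days may shift slightly, these are best read as about 14 days, and about 14 to 28 days in Cycle 1.

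**Share of infusions affected**

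Over C whole cycles there are 2C infusions, of which C fall on Day 15, so the share is C/2C = one half whatever C is. Over the planned six cycles it is 6 of 12. The Day 1 infusions from Cycle 2 have a same-day test.

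**Timing against the DLT assessment**

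The first on-treatment urinalysis is at Cycle 2 Day 1, which is day 29 counting from the first dose as day 1. Two infusions (days 1 and 15) have been given by then. By column position the Part D DLT assessment is marked at Cycle 1 Day 23, that is 29 − 23 = 6 days earlier. Whichever late Cycle 1 day is meant, it comes before the first on-treatment urine result.

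**Effect of adding one test before each Day 15 infusion**

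Over six cycles, leaving out Visit 801, scheduled urine tests rise from 6 (screening plus five Day 1 tests) to 12. Day 15 infusions resting on a scheduled result 14 or more days old fall from 6 to 0.

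**The case against.** The strongest reply is that nothing is broken. Section 9.5.3.3 sets no frequency, its general duty allows unscheduled tests, and Attachment 1 does provide recurring urinalysis. No text in the protocol says 28 days is too long. This stands: a reader might infer that the schedule violates the protocol's own rule, and the documents do not support that.

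Nor does the one-half share measure harm. It follows directly from two infusions and one test per cycle. Neither document gives a rate of proteinuria at the hold threshold, and in about 18 patients the number of infusions wrongly given could be zero.

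Other safeguards narrow the risk. Exclusion criterion 26(j) screens out marked proteinuria at entry. Day 14 chemistry includes albumin, creatinine, total protein and cholesterol, which bear on nephrotic syndrome. Section 9.5.3 requires a delay or reduction for clinically significant ramucirumab toxicity. None of these supplies a urine protein value before Day 15.

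A further objection is sound and shapes the remedy. A dipstick only triggers a 24-hour collection, and the hold acts on the result of that collection. No text withholds the infusion in the meantime, so an extra dipstick alone would not close the gap.

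A reader might also extend the point to blood pressure, because the vital signs comment reads "Starting in Cycle 3, to be performed once per cycle". That reading is not supported. Vital signs are marked on Day 14 in Cycles 1 and 2. Section 9.5.3.2 calls for blood pressure monitoring during treatment and suspension for severe hypertension. And "Ramucirumab in Part D will be administered intravenously at the investigational site", where a reading is immediate.

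**Conclusion.** The point holds as a cheap improvement to the schedule. Every Day 15 infusion, half of all infusions at any whole number of cycles, rests on a scheduled urine result about 14 days old (about 14 to 28 days in Cycle 1), and no on-treatment urine protein is scheduled before the Cycle 1 DLT assessment.

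This assumes nominal cycle timing, a site that performs only the scheduled tests, and marks read by column position in a table extracted from PDF. The count covers the main treatment period, not the extension.

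The DLT consequence is limited. Persistent proteinuria would be found at Cycle 2 Day 1, at about the time of the safety review that follows Cycle 1 (Section 12.2.14). Only proteinuria that arises and resolves within Cycle 1 would be missed altogether, and the documents do not say how likely that is. Section 5.1.5.2 records that Part D was still enrolling at Amendment (e), so the change could still reach patients.

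**What to change.** Make three linked changes.

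1. In Attachment 1, Part D, mark a urine protein dipstick before the Day 15 infusion of every cycle: preferably at the Day 14 visit where one is scheduled, otherwise on Day 15 before the infusion.
2. Exempt this test from footnote l for as long as ramucirumab continues.
3. Add to Section 9.5.3.3 that when a dipstick is 2+ or more, the infusion is withheld until the 24-hour result is available.

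The existing thresholds and dose levels stay as they are; the third change is a new dosing instruction and should be labelled as such.

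The cost is an amendment to the schedule table and one sentence in 9.5.3.3, one dipstick per cycle in about 18 patients who already attend for the infusion, and an occasional delayed infusion. Delays may recur in a patient admitted under criterion 26(j) with a 2+ dipstick and a 24-hour value below 1000 mg, since such a patient could reach 2+ at each test.

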9.5.3.4. Hepatic Encephalopathy

In the case of a new occurrence of hepatic encephalopathy and/or hepatorenal syndrome, ramucirumab will be discontinued.

9.6. Continued Access to Study Drug

Because LY2157299 is an investigational agent, patients cannot receive LY2157299 without being in a clinical trial. Ramucirumab is commercially available for other indications, but patients with HCC cannot receive ramucirumab without being in a clinical trial. Sorafenib is commercially available within the studied indication and will not be provided by the Sponsor outside of this clinical trial.

9.7. Blinding

This is an open-label study.

9.8. Concomitant Therapy

No other anticancer therapy, immunotherapy, hormonal cancer therapy, or experimental medications will be permitted while the patients are participating in this study. Palliative radiation therapy to nontarget lesions is allowed. Any disease progression requiring other forms of specific antitumor therapy will be cause for early discontinuation of study therapy.

Immunosuppressive agents for patients who have received a liver transplant are allowed if the patient is receiving these drugs as a maintenance treatment after transplant (Perry and Neuberger 2005). Rapamycin analogues are not allowed.

During the first-in-human Study JBAH, patients received EIAEDs, such as carbamazepine, phenobarbital, or phenytoin. No apparent drug-drug interaction has been observed, consistent with the nonclinical absorption, distribution, metabolism, excretion (ADME) properties of this agent.

When sorafenib is administered, avoid concomitant use of strong CYP3A4 inducers (such as, carbamazepine, dexamethasone, phenobarbital, phenytoin, rifampin, rifabutin, St. John's wort), when possible, because inducers can decrease the systemic exposure to sorafenib. Warfarin is not recommended in coadministration with sorafenib.

For Part D, patients may not receive chronic antiplatelet therapy, including NSAIDs (eg, indomethacin, ibuprofen, naproxen, nimesulide, celecoxib, etoricoxib, or similar agents) or other antiplatelet agents (eg, clopidogrel, ticlopidine, prasugrel, dipyridamole, picotamide, indobufen, anagrelide, triflusal, or similar agents). Patients receiving therapeutic anticoagulation with warfarin, low-molecular-weight heparin, or similar agents are excluded from participation. Anticoagulant therapy may be instituted during the course of treatment on study (following an asymptomatic or treatable deep vein thrombosis or pulmonary embolism), provided that no evidence of portal hypertension (including splenomegaly) or any prior history of variceal bleeding exists. Aspirin at dosages up to 100 mg/day is permitted.

9.9. Treatment Compliance

Patient compliance with study medication will be assessed at each visit. Compliance will be assessed by direct questioning, review of diary, and counting returned tablets. Deviations from the prescribed dosage regimen should be recorded in the "Study treatment: modifications" form.

For patients who are significantly noncompliant (<80% or >120% of expected study drug taken in a visit interval), investigative sites must counsel patients on the importance of study drug compliance and drug accountability. Patients who are consistently out of the compliance range may be discontinued. A Lilly representative should be contacted upon the second instance of treatment noncompliance.

The following procedures will be employed to assure appropriate drug accountability:

- Drug accountability will be emphasized at the start-up meeting.
- Drug accountability will be monitored throughout the study.
- Each patient should be instructed to return all study-drug packaging and unused material to the study site at each visit. The study site will keep a record of all drug dispensed to and returned by the patients throughout the study. Study site personnel will return or destroy (as requested) all unused study drug for all patients.
- Patients will keep a study diary to document that they are taking LY2157299 and sorafenib (if applicable) correctly.

Ramucirumab in Part D will be administered intravenously at the investigational site, under the direction of the investigator. As a result, a patient's compliance with study drug administration is ensured.

10. Efficacy, Health Outcome/Quality of Life Measures, Safety Evaluations, Sample Collection and Testing (Standard Laboratory Testing, Pharmacokinetics, Biomarker Analysis), and Appropriateness of Measurements

Refer to the Study Schedule in [Attachment 1](#) for study procedures and their timing.

Terms used to describe the study periods are defined below:

- **Baseline/Visit 0:** From the time of screening to first study treatment (or discontinuation, if no treatment is given)
- **Treatment Start:** First day of study treatment
- **Study Treatment Period:** Time from treatment start to discontinuation from study treatment
- **Discontinuation from Study Treatment:** The day the patient discontinues study treatment (summary visit)
 - **Applies to patients in extension period, too**
- **Postdiscontinuation from Study Drug 30-day Follow-up Period:** The time after the patient discontinues study treatment during which follow-up data are collected. Visit 801 starts 1 day after discontinuation from study treatment and lasts 30 days (± 3 days).
 - **Applies to patients in extension period, too.** However, for patients in the extension period, the end of the 30-day follow-up period is also the end of their study participation (unless further follow-up is required for safety reasons).
- **Long-Term Follow-up Period:** All subsequent long-term follow-up visits will occur at 60-day intervals (± 7 days) (for example, Visit 802, Visit 803, etc.) until the patient meets the requirements to discontinue from the study. These are the preferred windows for follow-up visits (Visit 802 and beyond); however, if some information cannot be obtained at all or not within the specified window for Visit 802 and beyond, it will not result in a protocol violation if no cardiac toxicity requiring further cardiac monitoring was observed at V801.
 - **Not required for patients in extension period (unless required for safety follow-up)**

